7.2. Procedures for handling withdrawal

Patients who withdraw or are withdrawn from this study will have the below information recorded:

- The reason(s) for their withdrawal
- Presence of any AEs and if so will be followed up by regular scheduled visits, telephone contact and correspondence until satisfactory clinical resolution of AEs is achieved.
- At least one follow-up contact (scheduled visit, telephone contact, correspondence) for safety evaluation during the 30 days following the last session of study treatment.
- In the event of pregnancy, the patient should be monitored until conclusion of the pregnancy and the outcome of pregnancy reported.

7.3. Patient replacement policy

After randomization and either the first rESWT treatment or the first sham-rESWT treatment, respectively, no patient will be replaced.

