4.8. Randomization and blinding of patients

- Patients that fulfill the inclusion criteria and do not fulfill any of the exclusion criteria will be randomly allocated to either rESWT + RP (n=20) or sham-rESWT + RP (n=20).
- Randomization will be performed as described by Rompe et al. (2008) in a randomized, controlled study on rESWT for Achilles tendinopathy. Specifically, a computerized random-number generator will be used to formulate an allocation schedule. Patients will be randomized to either treatment (rESWT + RP or sham-rESWT + RP), with use of the method of randomly permuted blocks. The randomization scheme will be generated with the use of the website, www.randomization.com. Fifty patients will be randomized into five blocks. A medical assistant at the clinic of the Principal Investigator will allocate interventions by means of opaque sealed envelopes that will be marked according to the allocation schedule. The medical assistant will be unaware of the size of the blocks.

- The randomized intervention assignment as outlined above will be concealed from both patients and health care staff until recruitment will be complete and irrevocable.
- Patients will be blinded in this study.
- The assessor will be blinded in this study. The assessor is the person who will assess the outcome of treatment during follow up. In this study, the assessor will be a medical assistant at the clinic of the Principal Investigator.
- The therapist will not be blinded in this study. The therapist is the person who will administer either rESWT or sham-rESWT to the patient. In this study, the therapist will be the Principal Investigator ([name]).

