4.9. Study treatment and visits

As outlined in Section 4.5 “Groups and treatments” above all subjects will perform RP that will last for eight weeks, independent of the individual time interval to return to play.

- The RP will start with a first visit to the clinic of the Principal Investigator during which clinical and ultrasonographic diagnosis will be performed. This first visit may take place on the day of injury (D0) or the first day (D1) or second day (D2) after injury (the sooner the better).
- After the first visit an individual number of days will follow until the fifth day after injury (D5) will be reached (acute phase). During this time the subject will apply the RICE principle (rest, ice, compression and elevation). Visits to the clinic of the Principal Investigator may be scheduled during this time but are not mandatory.
- On D5 the subacute/regeneration phase of the RP will start, with three visits per week to the clinic of the Principal Investigator (outlined in detail in Section 4.5 “Groups and treatments” above). The exact time for progression from the subacute/regeneration phase to the functional phase of the RP will be individually determined, depending on whether the criteria for progression will be fulfilled. During the functional phase there will also be three visits per week to the clinic of the Principal Investigator.
- Study treatments (rESWT or sham-rESWT) will start on D5. Each subject will be treated with nine sessions of rESWT or sham-rESWT, with three sessions per week. Accordingly, study treatments may take place at D5, D7, D9, D12, D14, D16, D19, D21 and D23.
- Six months after inclusion into the study there will be a separate visit for evaluating patient's satisfaction with the treatment outcome.

The time interval necessary for reaching return to play will be as follows:

- Based on our experience we expect that approximately 75% of the subjects treated with rESWT + RP will reach return to play within five weeks after D0.
- Furthermore, we expect that only approximately 25% of the patients treated with sham-rESWT + RP will reach return to play within five weeks after D0.

The Principal Investigator will perform the following procedures at the first visit:

- check eligibility
- obtain informed consent
- perform randomization
- collect patient's demographics & medical history

Furthermore, the Principal Investigator will perform the following procedures at all visits:

- record any concomitant medication

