- As outlined in Section 4.11.2. "Secondary clinical outcomes" above, one secondary clinical outcome will be assessment of patient's satisfaction at six months after inclusion into this study (using a scale ranging from 0 [maximum dissatisfaction] to 10 [maximum satisfaction]). This secondary clinical outcome will return a single data point (on a scale ranging from 0 to 10) for each patient, which is not normally distributed data. Accordingly, we will report inter-quartile ranges of this variable. Comparison between groups will be performed using the nonparametric Mann-Whitney test.
- As also outlined in Section 4.11.2. "Secondary clinical outcomes" above, another secondary clinical outcome will be presence or absence of re-injury during a time period of six months after inclusion into the study. This secondary clinical outcome will return a single data point ("yes" or "no") for each patient, which is not normally distributed data. Accordingly, we will report absolute and relative numbers of "yes" and "no" of this variable. Comparison between groups will be performed using Fisher's exact test.
- The probability value of less than 0.05 (p-value < 0.05) will be considered as statistically significant (Lang & Secic, 2006).
- All calculations will be performed using GraphPad Prism (version 5.00 for Windows, GraphPad Software, San Diego, CA, USA).
- All main conclusions of the study will be based on analyses of intention to treat rather than analyses of treatment. Note that there are various available methods for handling missing data in clinical trials (European Medicines Agency, 2010). In case of missing data (*i.e., in case a patient will withdraw or will be lost during the treatment or the follow-up periods*) we will determine together with the statistics experts at the Institute for

Medical Informatics, Biometry and Epidemiology (IBE) at the Ludwig-Maximilians-University of Munich (Munich, Germany) the most appropriate method for performing analyses of intention to treat. After randomization and the first rESWT or placebo treatment, no patient will be replaced.

- All efforts will be made to keep the proportion of patients lost to follow-up too small to affect the main findings of this study.
- Patient-centered care throughout this study will ensure that no patients will be lost to follow-up, or the number of patients lost to follow-up will be so small that findings would be unaffected by their inclusion.

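### The bar on replacement starts at the first session, not at randomization, so by implication a patient randomized on D0–D2 stays replaceable until D5, possibly with the arm known

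*Protocol*

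**What the plan says.** **Replacement.** Section 7.3: "After randomization and either the first rESWT treatment or the first sham-rESWT treatment, respectively, no patient will be replaced". Section 5 has the same cut-off: "After randomization and the first rESWT or placebo treatment, no patient will be replaced". Both conditions, randomization and a first session, must be met before the bar applies.

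**Analysis basis.** The same bullet of Section 5 says: "All main conclusions of the study will be based on analyses of intention to treat rather than analyses of treatment".

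**Timing.** Section 4.9 on the first visit: "This first visit may take place on the day of injury (D0) or the first day (D1) or second day (D2) after injury". It then says "The Principal Investigator will perform the following procedures at the first visit", and that list includes "perform randomization". On the sessions: "Study treatments (rESWT or sham-rESWT) will start on D5".

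**Roles.** Section 4.8: "The therapist will not be blinded in this study". It names the Principal Investigator as the therapist. Section 7.1 lets the Principal Investigator withdraw a patient at any time, at discretion. Section 4.8 also has a medical assistant allocate by opaque sealed envelopes, and says the assignment stays hidden from patients and staff until recruitment is final.

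**The concern.** Under intention to treat, a patient belongs to the assigned arm from the moment of randomization. A replacement rule that takes effect only some days later leaves a period in which a randomized patient can give up the place to someone else. If the replaced patient then leaves the analysis, the comparison is no longer between the groups that randomization formed.

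Replacement unrelated to arm and prognosis would cause little bias. The risk is selective replacement: patients who look slow to recover leave one arm, or patients who look quick leave the other. Either would move the primary outcome, days to return to play, towards a difference that the treatment did not cause. The protocol leaves room for this in two ways. The person with discretion to withdraw patients is unblinded, and the period ends at the Section 4.5 check on day five, which gives an early impression of recovery.

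**Working it through.** **1. Length of the gap.** First session on D5, randomization on D0 to D2 (Section 4.9): 5 − 2 = 3 days to 5 − 0 = 5 days. Section 4.4 excludes only patients injured more than seven days before enrolment. A patient first seen later than Section 4.9 foresees would therefore have a shorter gap or none.

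**2. Could the arm be known in the gap?**
- Section 4.9 lists randomization among the Principal Investigator's own first-visit tasks.
- Section 4.8 gives the envelopes to a medical assistant and promises concealment until recruitment is final.
- If that promise covers the whole trial, it cannot be kept, because the therapist must know each patient's arm from that patient's first session.
- If it is read patient by patient, it protects the time up to enrolment and says nothing about the days from then to D5.

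No sentence withholds the arm until the first session, and none says that it is disclosed earlier.

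**3. Does the fix affect the sample size?** The replacement rule carries no figure of its own, so the check is on Table 3 (Section 5.1): 20 per arm, 75% against 25%, two-sided 5%, stated power 91.8%.

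Power = Φ{[|p₁ − p₂| − 1.96·√(2·p̄(1 − p̄)/n)] / √[(p₁(1 − p₁) + p₂(1 − p₂))/n]}

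= Φ{[0.50 − 1.96·√(2 × 0.25/20)] / √(0.375/20)} = Φ{(0.500 − 0.310)/0.137} = Φ(1.39) = 91.7%.

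This reproduces the stated value. None of its inputs depends on when the replacement bar starts.

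**4. Size of the possible bias (illustration).** The documents give neither a number of replacements nor the predictive value of early signs, so both are assumed. The set-up is no true effect, 20 analysed per arm, and the two-sided Mann-Whitney test at 0.05. Outcomes are on a normal scale, which is harmless for a rank test. An early impression has correlation ρ with the outcome. In one arm 20 + k patients enter, and the k who look slowest are removed. There were at least 20,000 simulated trials per setting.

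| Replaced in one arm | ρ = 0.3 | ρ = 0.5 | ρ = 1 (perfect prediction) |
|---|---|---|---|
| 0 | about 5% | about 5% | about 5% |
| 2 | about 5.2% | about 5.7% | about 8.5% |
| 3 | about 5.4% | about 6.5% | about 12% |
| 5 | 6% to 6.5% | about 8% | about 20% |

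Replacing the slowest of the first 20 with unselected newcomers gives similar figures: at ρ = 0.5 about 6%, 6.5% and 7.5%; at ρ = 1 about 8.5%, 11.5% and 17%.

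Selection in both arms has more effect. If the slowest-looking are replaced under rESWT and the quickest-looking under sham, ρ = 0.5 gives 8.3% with two replaced per arm and 10.8% with three per arm. Most of the excess favours rESWT: 7.6 of the 8.3 points in the first of these.

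**The case against.** Several stronger readings are tempting, and the documents do not support them.

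- **That someone who knows the arm will replace patients.** Section 4.8 provides sealed envelopes, a medical assistant and a concealment statement, and the therapist needs the arm only at the first session. Early knowledge is possible because Sections 4.8 and 4.9 conflict and nothing rules it out, but it is not stated.
- **That intention to treat is broken.** No sentence says that a patient will be replaced before D5 or that a replaced patient leaves the analysis. The fixed 20 per arm points that way, but the analysis set may be defined in the SAP. Sections 7.1 and 7.2 also require reasons for withdrawal to be recorded and observations to be completed as far as possible, so removals should be traceable. What stands is that the rule permits something the stated analysis basis does not.
- **That type I error would reach 8.5% to 20%.** That requires perfect prediction of return to play by D5. Section 1 says imaging findings do not correlate directly with recovery time in an individual injury and stresses wide variation between patients. Section 4.9 makes clinic visits before D5 optional. With weak prediction and few replacements the inflation is small.
- **That the 50-patient schedule for 40 patients is a stock of replacements.** The protocol gives no purpose for the surplus, and Section 4.8 says the method follows an earlier Achilles tendinopathy trial. A balanced list would leave 50/2 − 20 = 5 spare places per arm. The mismatch is a separate inconsistency.
- **That the day-five check is a removal step.** Section 4.5 speaks of reconsidering the extent of the damage and of orthopedic attention, not of removal or replacement.

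These points limit the claim. They do not close the gap, which follows from the dates and the two replacement sentences.

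**Conclusion.** The point holds as a defect in a stated rule. For patients who follow the Section 4.9 schedule, replacement is not barred during the three to five days between randomization and the first session. That does not fit the intention-to-treat basis in Section 5. The dates and the wording are certain. Replacement in that period is permitted only by implication, and knowledge of the arm is possible but not stated.

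The harm depends on selective replacement. With 2, 3 or 5 replaced in one arm and a correlation of 0.5, type I error would be about 5.7%, 6.5% and 8% instead of 5%. The figures of about 8.5%, 12% and 20% are the upper end for replacement in one arm, under perfect prediction. The number replaced, the correlation and the arm are all assumptions. This should be corrected because it opens a route to bias that is easy to close; there is no evidence that anyone plans to use it.

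**What to change.** 1. In Sections 5 and 7.3, state that no patient is replaced after randomization and that every randomized patient is analysed in the assigned arm.
2. Reconcile Sections 4.8 and 4.9 on who carries out the allocation and when, so that the arm is revealed to the therapist only immediately before the first session.
3. Separately, reconcile the 50-patient schedule in Section 4.8 with the 40 patients planned in Sections 4.6 and 4.8.

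The first change costs one sentence in each of two sections, and the planned 20 per arm stays as it is. The drawback is that a patient who drops out between randomization and D5 counts within the 40, so a little information may be lost. That is the ordinary price of intention to treat.

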7.4. Medications permitted or not permitted during this study

No other adjunct specific treatment for acute HMC injury Type 3b is allowed during the duration of the study. Other medications not permitted are as explained in the Exclusion Criteria. Medications permitted are those not mentioned in the Exclusion Criteria.

8. Ethical Consideration

The researchers have considered the ethical issues that may arise with the conduct of this study. This trial will only be conducted after seeking approval from the Ethics Committee of the Universidad Abierta Interamericana (Buenos Aires, Argentina).

9. Patient Withdrawal & Compensation

Participation in this study is completely voluntary. The participants will not be paid for joining this study nor will they be expected to pay to join this study. Participants are able to withdraw themselves from this study at any time without any reason and consequences to their follow-up treatments. Standard routine care will still be provided to them. The researchers hold the right to use any data collected until a participant would withdraw from this study.

10. Adverse Events

10.1. Definitions

Adverse event (AE)

Any untoward medical occurrence in a patient administered an investigational product and which does not necessarily have a causal relationship with treatment. An AE can therefore be any unfavourable and unintended sign, symptom, laboratory observation or disease temporarily associated with the use of the investigational products, whether or not related to the investigational products.

The following should be reported as AE:

- Treatment emergent symptoms which include:
 - medical conditions or signs or symptoms that were absent before starting study treatments, and
 - medical conditions or signs or symptoms present before starting study treatments and worsen (increase severity or frequency) after starting study treatments.
- Abnormal laboratory values or tests that induce clinical signs or symptoms or require therapy.
- Any adverse experience even if no rESWs have been administered.

Any doubtful event should be treated as an AE.

Unexpected adverse event

Any adverse event not reported in the safety section of the Investigator's Brochure or if the event is of greater frequency, specificity or severity.

Serious adverse event (SAE)

Any adverse event occurring that:

- results in death, or
- is a life threatening adverse experience defined as any adverse event that places the patient, in the view of the Principal Investigator, at immediate risk of death from the

reaction as it occurred (note that this does not include a reaction that, in case it would have occurred in a more severe form, would have caused death, and/or

- results in patient hospitalisation or prolongation of existing hospitalisation.

The following hospitalisations are not considered to be SAEs:

- those planned before entry into the study,
- elective treatment for a condition unrelated to study indication or study treatment,
- those that occur on an emergency outpatient basis and do not result in admission (unless fulfilling other criteria in SAE definition), and
- parts of normal treatment or monitoring of this study indication and are not associated with any deterioration in condition.

Furthermore, the following events are not considered to be SAEs:

- those that result in a significant or persistent disability or incapacity defined as any event that results in a substantial and/or permanent disruption of the patient's ability to carry out normal life functions,
- those that are a congenital anomaly or birth defect,
- those that are any instance of overdose, either accidental or intentional (suspected or confirmed), and
- any other important medical event, based upon appropriate medical judgement, that may jeopardise the patient or may require medical or surgical intervention to prevent or avert one of the outcomes listed above.

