10.2. Detecting and documenting AE

Information about all AEs, whether volunteered by the patient, discovered by investigator questioning or detected through physical examination, laboratory test or other means, will be recorded on the Adverse Event Page of the CRF and followed up as appropriate.

Each AE will be described by:

a) Nature of AE

This will be documented in terms of a medical diagnosis(es). When this is not possible, the AE will be documented in terms of signs and/or symptoms observed by the Principal Investigator or reported by the patient.

b) Duration of AE

Start and end dates will be documented.

c) Assessment of causality

The Principal Investigator will attempt to explain each AE and assess its relationship, if any, to the study treatments. Causality should be assessed using the following definitions:

• Very likely

- The AE follows a reasonable temporal sequence from study treatments administration,
- abates upon discontinuation of study treatments, and
- reappears on repeated exposure (re-challenge).

• Probable

- The AE follows a reasonable temporal sequence from study treatments administration,
- abates upon discontinuation of study treatment, and
- cannot reasonably be explained by known characteristics of the patient's clinical state.

• Possible

- The AE follows a reasonable temporal sequence from study treatments administration,
- but could have been produced by the patient's clinical state or other mode of therapy administered to the patient.

• Doubtful

- The temporal association between study treatments and AE is such that the study treatments are not likely to have any reasonable association with the observed event.

• Very unlikely

- The AE is definitely produced by the patient's clinical state or other mode of therapy administered to the patient.

The degree of certainty with which an AE is attributed to study treatments or alternative cause like natural history of disease or concomitant treatment will be guided by the following considerations:

- time relationship between treatment and occurrence of AE,
- de-challenge and re-challenge information, if applicable,
- dose response relationships,
- lack of alternative explanations, i.e. no concomitant drug used and no other inter-current disease,
- reaction of similar nature being previously observed with the study treatments, and
- reaction having often been reported in the literature for the study treatments.

d) Severity of AE

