- **Mild:** awareness of signs or symptoms, but they are easily tolerated.
- **Moderate:** enough discomfort to cause interference with usual activity.
- **Severe:** incapacitating, with inability to work or do usual activity.

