10.3. Reporting of SAE

Information about all SAE will be recorded on the Serious Adverse Event Section of the CRF. All events documented in the SAE Form must be reported within 24 hours to ANMAT

Any death or congenital abnormality, if brought to the attention of the Principal Investigator within six months after cessation of study treatments, whether considered treatment related or not, should be reported to ANMAT

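### Section 10.1 of the protocol classes disabling and other important medical events as non-serious, which takes them out of the 24-hour report to the authority; the list heading appears to be inverted

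*Protocol*

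**What the plan says.** Section 10.1 of the protocol gives three criteria for an SAE. The event causes death, it puts the patient at immediate risk of death, or it "results in patient hospitalisation or prolongation of existing hospitalisation".

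Two lists of exceptions follow. The first concerns hospitalisations and exempts, among others, "those that occur on an emergency outpatient basis and do not result in admission (unless fulfilling other criteria in SAE definition" (the bracket closes there). The second opens with "Furthermore, the following events are not considered to be SAEs" and has four items:

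- events described as "those that result in a significant or persistent disability or incapacity";
- congenital anomaly or birth defect;
- any overdose, whether accidental or intentional;
- any other important medical event that may put the patient in jeopardy or "may require medical or surgical intervention to prevent or avert one of the outcomes listed above".

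Section 10.2 says that every adverse event "will be recorded on the Adverse Event Page of the CRF and followed up as appropriate". Its top severity grade is "incapacitating, with inability to work or do usual activity".

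Section 10.3 sets the expedited report: "All events documented in the SAE Form must be reported within 24 hours to ANMAT". It separately asks for any death or congenital abnormality to be reported to the authority if it becomes known within six months after study treatment ends. Section 10.4 has pregnancies reported as SAEs.

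**The concern.** The four items in the second list read like the rest of a definition of seriousness, yet they stand under a heading that denies them that status. The last item shows it best. An event needing intervention to avert an outcome listed above is described by its closeness to the serious outcomes, which makes little sense as a ground for exemption.

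The SAE label decides what goes on the SAE Form, and the form decides what reaches the authority within 24 hours. Staff who follow section 10.1 literally would therefore send no expedited report of a disabling injury managed without admission.

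Safety is part of the general objective (section 3.1). Participants are 18 to 35 years old (section 4.3) and treated at clinic visits (section 4.9). It is a fair inference, though not a figure in the protocol, that death, threat to life and admission will be uncommon. Serious harm could then well fall in the excluded categories. The protocol itself foresees problems that need not lead to admission: persistent numbness sent to a neurologist (section 10.6), and more extensive tissue damage or haematoma that may need an orthopaedic surgeon (section 4.5).

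**Working it through.** No rate, power or sample size is involved, so the check is to trace each kind of event through sections 10.1, 10.3 and 10.4.

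| Event | Three SAE criteria (10.1) | Negative list (10.1) | Report to the authority |
|---|---|---|---|
| Disability or incapacity, without death, threat to life or admission | not met | named as not an SAE | none expedited |
| Disability or incapacity, with admission | met | named as not an SAE | two contradictory answers |
| Other important medical event, treated as an emergency outpatient without admission, no threat to life | not met | named as not an SAE | none expedited |
| Congenital anomaly | not met as such | named as not an SAE | required by 10.3, no time limit stated in that sentence |
| Overdose | not met as such | named as not an SAE | none expedited; intended status not settled |
| Pregnancy | not met as such | not named | reported as an SAE under 10.4 |

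Four things follow.

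1. **The two lists collide.** The negative list has no clause saying that the three criteria take precedence. A disabling event with admission is an SAE by the first list and not an SAE by the second.
2. **The proviso on outpatient care is nearly empty.** Emergency care without admission is exempt unless another SAE criterion is met. Admission is already ruled out, so only death and threat to life remain. An important medical event handled this way gains nothing from the proviso and is then named in the negative list as well.
3. **Sections 10.3 and 10.4 do not match 10.1.** Congenital abnormality is not an SAE in 10.1 but must be reported to the authority in 10.3. Pregnancy is reported as an SAE in 10.4, although on its own it meets none of the three criteria.
4. **Nothing restores the lost report.** Section 10.2 sends all adverse events to the CRF but states no deadline. Section 10.5 covers notices from the manufacturer and the Ethics Committee's own procedures; it creates no report to the authority.

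Count of the negative list: 2 categories with no substitute report to the authority (disability; important medical events) + 1 with a report but no stated deadline (congenital anomaly) + 1 of unsettled status (overdose) = 4.

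**The case against.** The strongest reply is that little is lost in practice. Doubtful events count as adverse events (10.1). All adverse events are recorded with nature, dates, causality and severity (10.2) and followed until they resolve or stabilise (10.4). Withdrawn patients have at least one safety contact in the 30 days after their last session (7.2), and the authority's monitors may inspect medical records (6.4). Section 10.5 passes on related events that are serious or unexpected to the Ethics Committee, and greater severity can make an event unexpected. The trial is small (20 + 20 = 40 patients), and the side effects it anticipates are bruising and temporary numbness. On this view the defect is a missing label for an event of unknown frequency.

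This limits the harm and should be granted: the events are not lost from the data. But none of these routes brings a timely report to the authority. The route in 10.5 starts with the manufacturer and ends at the Ethics Committee.

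Some narrower objections have merit.

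- The outpatient exemption concerns what counts as a hospitalisation. It does not itself classify important medical events; the negative list does that.
- The sentence on congenital abnormality in 10.3 directly follows the 24-hour rule and also covers death, so it can be read as extending the reporting window. The missing deadline is therefore a minor point, and the handling of pregnancy covers much of that route.
- The inversion is inferred. The wording of the last item supports it best; for disability it rests mainly on position in the list.

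The contradictions do not depend on that inference. They stand on the text as written.

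**Conclusion.** The concern holds, and the text must be corrected. Followed literally, section 10.1 with section 10.3 withholds SAE status and the 24-hour report from disabling and other important medical events that involve no death, threat to life or admission. Where there is admission, the section gives two answers for a disabling event.

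Of the four categories under the negative heading, two lose expedited reporting to the authority outright. Recording and follow-up of adverse events continue, and the planned efficacy comparisons are not affected. The protocol gives no basis for predicting how many events would be involved, and none is claimed.

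The conclusion assumes only that staff apply section 10.1 as written when deciding what goes on the SAE Form. That the heading was inverted by mistake is the likely explanation, but it is not needed for the conclusion.

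**What to change.** In section 10.1:

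- delete the second negative heading;
- list disability or incapacity, congenital anomaly and other important medical events as SAE criteria beside the existing three;
- state whether an overdose is always an SAE or only when it meets another criterion;
- keep only the hospitalisation exemptions as exclusions.

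Then reconcile 10.1 with 10.3, giving a time limit for the congenital abnormality report, and with the pregnancy rule in 10.4. Check the SAE and adverse event fields of the CRF, which is not among the documents, against the corrected definition.

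The cost is one paragraph of protocol text and the matching CRF fields. The only downside is possibly a few more expedited reports.
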